Dextromethorphan in Fibromyalgia (F161018005) Study Protocol

Key Personnel

- [name]
 - Principal Investigator
 - [name] has extensive experience in conducting longitudinal treatment studies in chronic multisystem illnesses. He is very familiar with recruiting and retaining participants with chronic pain and fatigue.
- [name]
 - Sub-Investigator (Study Physician)
 - [name] is an active clinician in the UAB Pain Treatment Clinic. Previously, he has served as a protocol medical director and is currently participating in several clinical protocols.
- [name]
 - Sub-Investigator
 - [name] is an active clinician in the 1979 clinic. She is currently working on multiple pain protocols as medical director. For this protocol, she will act as external medical review.
- [name]
 - Project Coordinator
 - [name] will be the project coordinator, and responsible for all aspects of the study: recruitment, consenting, retention will supervise all the students.

Purpose

The overall objective of this protocol is to test if DXM can suppress symptoms associated with Fibromyalgia. DXM is used in multiple over the counter cough suppressants. We will be observing the effects of DXM. If one of these medications help the symptoms of FM, it will give us information about what is wrong in people with FM.

Background

Fibromyalgia (FM) is a chronic widespread pain syndrome. Those impacted by this syndrome experience pain, fatigue, sleep issues, cognitive impairment, headaches, among other symptoms. Fibromyalgia (FM) affects approximately 5% of all women in the United States. Current treatment options are limited because its pathophysiology is not currently understood. Many patients suffer with decreased quality of life and loss of employment due to this illness.

We do not understand the precise mechanism of Fibromyalgia, and we do not yet have a targeted treatment for the condition. A way to treat the symptoms of FM is paramount as other research concurrently attempts to understand the mechanisms behind the disease. There is current ongoing study of [name] that is taking daily blood draws for 25 consecutive days in an attempt to identify the underlying biomarker for Fibromyalgia.

DXM has been used in previous research and have been shown to suppress pain symptoms. An example of this previous research comes from Morel et.al. by which low dose DXM was administered and evaluated pain and cognitive function in rats with spinal cord injuries. This animal model demonstrated DXM has a favorable impact on neuropathic pain.

Previous literature has suggested that dextromethorphan at 0.1mg/kg intraperitoneally reduces central inflammation (Chechneva et al., 2011 – link below). This dosage would translate to approximately 8mg for an average U.S. female weighing 166 pounds. Our dosage of 20mg has been adjusted up to account for rapid first-pass metabolism when administered orally.

In this study, we will be administering no more than a daily dose of DXM (20 mg) to observe the possible suppression of symptoms in Fibromyalgia.

References

1) Mease, P. (2005). Fibromyalgia syndrome: review of clinical presentation, pathogenesis, outcome measures, and treatment. *The Journal of Rheumatology*, *75*, 6-21.

4) Jacob Ablin, Lily Neumann, Dan Buskila, Pathogenesis of fibromyalgia – A review, Joint Bone Spine, Volume 75, Issue 3, May 2008, Pages 273-279

Participants (Screening and Selection)

15 participants with fibromyalgia (FM) will be recruited into this study.

- Sex: Female
- Race/Ethnicity: Any
- Age: 23-65
- Health status: 15 individuals with Fibromyalgia

Inclusion Criteria

- 1. Age 18-65, inclusive;
- 2. Meet the 1994 Case Definition criteria for CFS (assessed through semi-structured interview and the DePaul University Fatigue Questionnaire) (attachment #7) & the Fibromyalgia criteria as outlined by American College of Rheumatology (2010).
 - a. Severe chronic fatigue ≥6 consecutive months not due to ongoing exertion or other medical condition associated with fatigue;
 - b. Fatigue interferes with daily activities and work (;
 - c. Reports \geq 4 symptoms that started with or after the fatigue, from:
 - i. Post-exertion malaise >24 hours;
 - ii. Unrefreshing sleep;
 - iii. Short-term memory or concentration impairment;
 - iv. Muscle pain;
 - v. Joint pain without swelling or redness;
 - vi. Headaches of a new type/pattern/severity;
 - vii. Lymph node tenderness;
 - viii. Frequent or recurring sore throat
- 3. FM symptoms for \geq 12 months;
- 4. Participant completes daily self-report during the baseline period;

5. Able to attend UAB for all scheduled appointments.

Exclusion Criteria

- 1. Blood draw contraindicated or otherwise not able to be performed;
- 2. High-sensitivity c-reactive protein (HS-CRP) \geq 10 mg/L;
- 3. Erythrocyte sedimentation rate (ESR) >60 mm/hr;
- 4. Positive rheumatoid factor;
- 5. Positive anti-nuclear antibody (ANA);
- 6. Levels of thyroid stimulating hormone or free thyroxine outside UAB lab reference values;
- 7. Diagnosed rheumatologic or auto-immune condition;
- 8. Blood or Clotting disorder;
- 9. Use of blood thinning medication;
- 10. Current use of MAOI
- 11. Daily Consumption of grapefruit juice
- 12. Oral temperature >100°F at baseline;
- 13. Febrile illness or use of antibiotics in the 4 weeks before study commencement;
- 14. Planned surgery or procedures during the study period, or operated on in the 4 weeks before study commencement;
- 15. Pregnant or planning on becoming pregnant within 6 months; or currently breastfeeding
- 16. Regular use of any anti-inflammatory medication (such as aspirin, ibuprofen, naproxen);
- 17. Significant psychological comorbidity that in the discretion of the investigator compromises study integrity and/or a baseline HADS depression subscale score of ≥16;
- 18. Current litigation or worker's compensation claim;
- 19. Current participation in another treatment trial;
- 20. Planned vaccination during the study period, or vaccinated in the 4 weeks before study commencement.

Recruitment

FM participants will be primarily identified from a database of past research participants in our lab. All such participants have provided permission and expressed interest in being contacted for future studies. Individuals will also be drawn from the local community around Birmingham via referrals from local physicians or from online advertisements.

We will primarily recruit by contacting individuals on our laboratory database; these are individuals with FM who have consented to being contacted about future studies. To recruit individuals with FM, we will also contact local physicians. After the subject's physician presents a brief summary of the study to the potential participant, it will be the responsibility of the potential participant to contact the research team in order to be screened for the study. Our research staff at UAB will not be accepting names or any PHI from the physicians. We will rely on potential study participants to contact us directly if they are interested in learning more about the research study. Participants will also be recruited from the community. Advertisements that are distributed to the public will also require an interested potential participant to contact the research team.

Telephone Screening

To minimize inconvenience to potential participants, the prescreening screening will be conducted over the telephone by a trained member of the research staff: the study aims, protocol, and any possible risks will be described and a series of questions will be asked to determine interest and eligibility for screening for the study. A request to obtain the participant information will be completed via a partial waiver document. Individuals refusing to participate or to provide PHI will be thanked for their time and asked if they want their contact details to be included in the research lab's database to be contacted for future research. If the answer is no,

then all information collected will be destroyed immediately. Following the telephone pre-screening, if the potential participant expresses interest and they are determined to be potentially eligible for the study, an appointment will be made for them to attend an in-person screening visit.

Study Visits

Visit Locations

- UAB Clinical Research Unit (CRU), [name]
- Campbell Hall, [name]

Visit 1 (In-Person Screening)

Individuals who satisfy the telephone pre-screening criteria will be invited to a comprehensive in-person screening session. These sessions will be conducted by the PI or trained research staff. Individuals will first undergo informed consent; the consent form will describe the necessary eligibility confirmation that takes place before proceeding with the full study. Consenting individuals will complete several self-report questionnaires, submit to an examination of their height, weight, and vital signs (blood pressure, heart rate, and temperature), and provide a blood sample to ensure eligibility per the study criteria. Participant will receive a hand held tablet and instructions on how to complete the daily questions via the tablet. Vital signs & blood draws will be taken by the CRU nursing staff, using standardized sterile techniques.

Once the blood test results are available from the UAB Hospital Lab they will be reviewed by the PI and study doctor to confirm eligibility. All eligible participants will be contacted by telephone by a member of the research staff. If a participant's test results do not meet eligibility criteria, the individual will be informed that they are ineligible to participate and asked to return the handheld tablet to the research team. Alternatively, potential participants will be given a self-addressed envelope to return the tablet if they are unwilling to return to the site.

Visit 2

Participants will return to the CRU or Campbell Hall after approximately 14 days following visit 1. At this visit, a member of the study team will conduct an open interview to review the daily at-home symptom reporting and general health since the first visit. Also at this time the study team will instruct the participants on how to take their study medication. The placebo will be purchased from a compounding pharmacy such as Double Oak Pharmacy in Birmingham, Alabama. The participants will receive their initial 5 weeks supply of medication, which is placebo (single-blind). Participants will not be told when they are taking placebo or DXM until the end of study. The participants will also continue to record their symptoms twice a day using the hand-held device throughout the duration of the study for the entire (~20 weeks).

Visit 3

Approximately 5 weeks after visit 2, the participant will return to the CRU so the nursing staff can record their vital signs and discuss any adverse events. The study staff will review their at home daily symptoms and receive DXM for approximately the next 5 weeks.

Visit 4

Approximately 5 weeks after visit 3, the participant will return to the CRU so the nursing staff can record their vital signs and draw 20cc of blood. The blood will be analyzed by the UAB Hospital lab to monitor the participant's liver & renal function. Also, at this visit the research team will review daily at-home symptoms & any adverse events. If any participant has experienced serious/severe adverse events the participant will be terminated from the study as to ensure there is no increased harm to the participant. If no adverse events have

been experienced the participant will receive the next dose of DXM to take for 5 weeks, and continue the athome daily symptom review using the hand-held device.

Visit 5

Approximately 5 weeks after visit 4, the participant will return to the CRU so the nursing staff can record their vital signs and draw 20cc of blood. The blood will be analyzed by the UAB Hospital lab to monitor the participant's liver & renal function. Also, at this visit the research team will review daily at-home symptoms & any adverse events. If any participant has experienced serious/severe adverse events the participant will be terminated from the study as to ensure there is no increased harm to the participant. If no adverse events have been experienced the participant will receive the normal dose of DXM to take for 30 days and continue the at-home daily symptom review using the hand-held device.

Visit 6

Approximately Two weeks after visit 5 the participant will return to the CRU or Campbell Hall to turn in their handheld device and have their final interview with the research staff. At this visit, [name] will review daily symptoms and general health since visit 10 and un-blind the participant to which medications were received during the study.

A +/- 3 day study visit window will be implemented for all study visits to allow for reasonable flexibility in the participant's schedule as well as staff availability.

At any time throughout the study, if a participant reports feeling unwell or having any adverse events from any of the supplements, a review will be conducted by the PI and study doctor. If necessary, appropriate medical management will be provided.

If any participant is terminated from participating in the study, they will be required to return the hand-held device and any unused medicine back to a member of the UAB research study staff.

Study Timeline

The participant will be involved approximately 20 weeks for the entire study; this includes the in person screening, daily symptom reporting which is 10 minutes per day or less, and study medication disbursement. All blood draws will be conducted at the CRU in Jefferson Towers. Study medication disbursement will occur at UAB Campbell Hall or CRU.

Week	Task	Visit		Money
1	Screening	V1	Blood Draw Screening Labs & assays	\$50
2	Baseline			
3	Baseline	V2		\$100.00
4	Placebo			
5	Placebo			
6	Placebo			
7	Placebo			
8	Placebo	V3		\$100.00
9	DXM			
10	DXM			
11	DXM			
12	DXM			

13	DXM	V4	Blood Draw Hepatic / Renal & Assays	\$100.00
14	DXM			
15	DXM			
16	DXM			
17	DXM			
18	DXM	V5	Blood Draw Hepatic / Renal & Assays	\$100.00
	Baseline no			
19	drug			
	Baseline no			
20	drug	V6	Blood for assays	\$100.00
			Total Compensation	\$550.00

Compensation

Participants will be compensated with cash at screening, and check or direct deposit at all remaining visit. Cash is necessary at the screening visit as it will allow for most exclusionary criterion to be detected. Participants can receive up to \$550 in compensation for completing the study:

- Visit 1 (in-person screening): \$50
- Visits 2-6: \$100

Biospecimens

Peripheral blood samples will be collected and appropriately processed by the Clinical Research Unit (CRU) staff.

Screening session protocol: A 21/23g needle will be used to collect a maximum of 60cc of blood into labeled blood collection tubes to conduct screening tests. This blood will be tested by the UAB Hospital Lab to ensure that the participant meets the study criteria. The screening tests will include: complete blood count, erythrocyte sedimentation rate, thyroid stimulating hormone, free thyroxine, c-reactive protein, antinuclear antibodies, rheumatoid factor, liver function tests, kidney function tests and human chorionic gonadotropin. The total amount of blood drawn per participant for all study visits is 120cc.

Baseline and drug monitoring phases: At the screening visit and 3 blood draws during the drug monitoring phase, we will test the levels of expressed cytokines in blood as a marker of immune activity. Blood will be drawn via venipuncture into one 8-10cc (approximately 2 teaspoons) vacutainer. The blood will be centrifuged and will be extracted and placed into cryovials. The cryovials will then be stored at -80°C until ready for analysis. All specimens will be collected and processed by the nursing staff and CCTS lab.

Specimens will be labelled with: 1) participant identification number (PID), (2) date of blood draw, 3) study identifier 4) study principal investigator. We will assign a 3-digit participant ID that is based on the order of the in-person screening. The number is assigned at the time of screening. The first person to be screened will be given number 001, preceded by the study identifier (DXM); the first participant will be DXM-001. The computer file linking the PIDs to personal information will be kept on a single computer in the office of the PI. The computer hard drive will be encrypted and password protected. The file itself will require a password for access. No specimens will contain personally identifying information.

Samples will be stored at -80C, for a period not exceeding 5 years after participant completion, for later use by study personnel. Use of the stored samples will be restricted to the condition under study that is identified in this protocol.

Risks and Benefits

Benefits

It is possible that some participants may experience an improvement in their symptoms. It is also possible that a better understanding of the mechanisms underlying FM will allow treatments to more effectively target the disease for current and future patients.

Risks

The physical risks of venipuncture include discomfort and bruising around the blood draw site. There is also the risk of infection. The risks associated with this study concern the discomfort associated with having blood drawn and receiving the Dextromethorphan.

Participants should not take Dextromethorphan (DXM) if they have been diagnosed with phenylketonuria (PKU) because it could contain phenylalanine, if they are currently using or have used an MAO inhibitor, or if they have one of the following conditions: chronic bronchitis, emphysema, asthma, diabetes, liver disease, and mucus with cough or slowed breathing. These will be reviewed at the during the phone screen, in person screening and throughout the study. Dextromethorphan is known to produce side effects in individuals which include: slight drowsiness / dizziness, nausea or vomiting. Rarely, severe drowsiness can occur, participants will be instructed to notify study staff if they experience any of these side effects.

Grapefruit juice interacts with Dextromethorphan, participants will be asked to not drink grapefruit juice for the duration of the study.

Dextromethorphan is known to produce side effects in individuals which include: diarrhea, dizziness, cough, vomiting, swelling in the hands, ankles and or feet. Rarely slight drowsiness can occur; participants will be instructed to notify study staff if they experience any of these side effects. The most severe possible complication is serotonin toxicity.

The participant may experience some discomfort, bruising and the possibility of infection at the site of the blood draw on visits 1,3,6,9. Bruising should be minimal and should go away with a 2-3 days of the blood draw. We will minimize these risks by having only certified nurses or trained phlebotomist conduct the blood draws using standard sterile techniques.

The risks associated with taking the study medications can be primarily be avoided through proper screening of the participant and having a clear understanding of the medication the participant takes, educating the participant to contact the study staff of any and all changes to their medication. If an adverse event or side effect arises, a determination of severity and proper medical care will be advised and depending on the severity of the symptom the participant would be removed from the study and an evaluation of how to continue would be made by the study staff.

Minimization of Risks

Our screening procedures will minimize the probability of enrolling a patient who has a greater than normal risk of suffering adverse events from the medication (DXM). Any remaining risks for adverse events will be reduced by several checks:

 The risks associated with the blood draw will be minimized by using trained and licensed CRU nursing staff to perform the blood draw. Standard sterilization procedures will be followed to minimize the risk of infection. The blood draw site will be examined carefully to ensure no adverse events have occurred, and it is safe to proceed.

- 2. A more thorough investigation of adverse events will be collected at each laboratory visit. This includes a qualitative open interview assessment of symptoms and general health during the preceding month.
- 3. Also, blood tests will be collected at the mid-point of each treatment condition (visits 1, 3, 6, 9) to monitor liver and kidney function.
- 4. The relatively short duration of each study medication treatment (10 weeks)
- 5. Participants will be explained the symptoms of serotonin syndrome/ toxicity and will be instructed to report to the study staff if any symptoms occur. Also, individuals that have experienced an allergic reaction to any of the medication used in this study will be excluded from participating during the prescreening or at Visit 1.

Procedures to Maintain Confidentiality

Name, contact information, and medical history (participant reported –no medical records) are required to assess safety and eligibility for the study. Personally identifying information will also be collected as an identification requirement for study procedures. Identifying information will be stored on a single computer that is encrypted, and password protected at both operating system levels, and at the file level. All data maintained on paper-based records will be locked in a file cabinet in a locked room in the lab of the PI accessible only to the research study team.

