Dextromethorphan in Fibromyalgia Statistical Analysis Plan

NCT #: NCT03538054

ID: F161018005

Version Date: 6/28/2022

Statistical Analysis Plan

Statistical analyses were performed in SAS software, Version 9.4 of the SAS System for Windows (SAS Institute Inc., Cary, NC, United States). The primary outcome was the difference in daily self-reported general pain during the last four weeks of placebo versus the last four weeks of DXM treatment. Normality testing was performed with Shapiro–Wilk tests. Participant outcome scores were meancentered by participant, allowing analyses to reflect within-person changes to the treatments, rather than between-person differences. A generalized estimating equations (GEE) model is fitted to predict daily symptom severity based on study condition (placebo, DXM), assuming the autoregressive correlation structure and normal distributions. The grouping variable was subject ID. Significance of the parameter estimates was assumed at p<0.05. There were no corrections for multiple comparisons.

The secondary outcome (self-reported physical activity) was tested using the same GEE approach. Additionally, exploratory analyses (highest pain, muscle pain, fatigue, and depressed mood) were tested in separate GEEs.

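### Staff who can infer the treatment review daily symptoms between the two primary windows, chiefly at Visits 3 and 4, with no bar on discussing the participant's self-rated outcome

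*Protocol*

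**What the plan says.** **Blinding.** Protocol, Study Visits, Visit 2: "The participants will receive their initial 5 weeks supply of medication, which is placebo (single-blind", and "Participants will not be told when they are taking placebo or DXM until the end of study". Neither document describes any blinding of staff.

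**Order.** Protocol, Study Timeline: every participant has baseline to week 3, placebo in weeks 4-8 and DXM in weeks 9-18.

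**Symptom review.**
- Visit 2: "a member of the study team will conduct an open interview to review the daily at-home symptom reporting and general health since the first visit".
- Visit 3: "The study staff will review their at home daily symptoms and receive DXM for approximately the next 5 weeks".
- Visits 4 and 5, in the same sentence each time: "Also, at this visit the research team will review daily at-home symptoms & any adverse events".
- Protocol, Minimization of Risks, item 2: an open-ended interview on symptoms and general health at each laboratory visit, presented as part of adverse-event assessment.

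**Outcome.** The participant rates her symptoms twice a day on a handheld device for about 20 weeks (Visit 2). SAP: "The primary outcome was the difference in daily self-reported general pain", comparing the final four weeks of each condition.

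No section scripts the symptom review, limits it to diary completeness, or tells staff not to discuss scores.

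**The concern.** The endpoint is the participant's own judgement of her pain. If someone who knows what she is taking talks with her about her recent ratings, tone, emphasis or choice of question can change how she rates afterwards. No intent is needed.

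The primary result is a within-person difference, so an influence that was equal in both conditions would cancel. This one need not be equal. Two of the reviews fall after the placebo ratings are complete and before the DXM ratings that count. Expectation conveyed at those visits would appear as a drug effect.

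**Working it through.** **1. Who can know the treatment.** No sentence says that staff know it. That follows from two facts: blinding is described for participants only, and the sequence is the same for everyone. The visit number therefore identifies the treatment.

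**2. Where the reviews fall.** Placebo runs over weeks 4-8, so its last four weeks are weeks 5-8. DXM runs over weeks 9-18 on the timetable, so its last four weeks are weeks 15-18. Each visit is taken to close the week in which the timetable lists it.

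| Visit | Week | Before placebo window? | Before DXM window? | What staff can infer |
|---|---|---|---|---|
| 2 | 3 | Yes | Yes | Placebo about to start; ratings so far are untreated |
| 3 | 8 | No, closes it | Yes | Placebo ending, DXM starting |
| 4 | 13 | No | Yes | Participant is on DXM |
| 5 | 18 | No | No, closes it | DXM ending on the timetable |

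One review precedes the placebo window and three precede the DXM window. The difference, 3 - 1 = 2, is Visits 3 and 4.

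**3. Visit 5.** The Visit 5 text supplies DXM for a further 30 days, whereas the timetable shows no drug in weeks 19-20. On the timetable, Visit 5 comes too late to affect the DXM window. On the Visit 5 text, ratings stop when the device is returned at Visit 6 in week 20. The last four weeks of DXM with ratings would then be weeks 17-20, and weeks 19-20 (two of the four) would follow Visit 5. The two places must be reconciled before Visit 5 can be classified.

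**4. How much time separates review and window.** Visits 2 and 3, and Visits 4 and 5, are about 5 weeks (35 days) apart. Using the last 28 days drops about 35 - 28 = 7 days after Visit 2 and after Visit 4. After Visit 3 the gap is weeks 9-14, about six weeks.

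**5. What the analysis does with a shift.** Let d be the true DXM-minus-placebo difference and b the extra shift in DXM-window ratings caused by staff contact. Centring subtracts the same personal mean m from both windows:

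(DXM mean + b - m) - (placebo mean - m) = d + b

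Centring therefore leaves b in place. Condition is the only predictor that the SAP names for the GEE, and with a single order nothing in the data separates b from d.

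**6. Illustration of sensitivity.** The documents give no pain scale, SD, effect size or power calculation, so there is no stated figure to reproduce. Inputs: n = 15 (Protocol, Participants) and alpha = 0.05 (SAP; two-sided assumed). A paired t-test stands in for the GEE. Set d = 0 and express b in SDs of the within-person difference. The test statistic is then noncentral t with 14 df and noncentrality b x sqrt(15) = 3.873b, and P(p<0.05) is the probability that it falls beyond the two-sided 5% limits.

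| Assumed b (SD) | Noncentrality | P(p<0.05), inert drug |
|---|---|---|
| 0 | 0 | 5.0% |
| 0.1 | 0.387 | 6.5% |
| 0.2 | 0.775 | 11.2% |
| 0.3 | 1.162 | 19.2% |
| 0.5 | 1.936 | 43.8% |

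The values of b are assumptions. The table shows how sensitive a trial of this size is to a given shift, not how large the shift is.

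**The case against.** **Ratings are entered at home by the participant.** Staff neither ask for nor record the scores. This stands as a real safeguard, so the participant blind is not the only protection. It prevents staff from altering entries, but not a conversation from affecting later ones.

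**The windows leave a lag.** About a week is dropped after Visits 2 and 4, and about six weeks pass between Visit 3 and the DXM window. Any influence has to last that long and then persist through 28 days of ratings. This stands as a reason to expect attenuation. It does not show that the influence is zero.

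**The interview serves safety.** Minimization of Risks ties it to adverse events, and Visits 4 and 5 pair symptom review with adverse events. Visit 2 also has an evident eligibility use, because completing the baseline diary is an inclusion criterion. This stands, and the interview should be kept. What is missing is narrower: uniform wording and an instruction not to discuss scores.

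**Stronger readings that the documents do not support.** A reader might infer that all of Visits 2 to 5 carry the same risk. They do not: Visit 2 concerns untreated ratings, and on the timetable Visit 5 closes the DXM window. A reader might also infer that the same individuals conduct every review, or that staff go through her scores with her each time. The protocol names staff only in general terms and does not say that scores are discussed; it merely does not prevent it. Finally, the 11% to 44% range might be taken as the trial's false-positive rate. It only restates what an assumed shift would do.

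**Conclusion.** The concern holds in limited form. There is an open, condition-specific route for staff expectation to reach the primary outcome, chiefly through Visits 3 and 4. Visit 2 is a lesser concern. Visit 5 matters only if DXM ratings continue after it, on which the protocol contradicts itself. Self-entry at home and the four-week windows reduce the risk without removing it, and the planned analysis cannot detect or correct it.

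The size is unknown. The documents show that bias is possible, not that it occurred, and they do not support saying that a positive result would be an artefact. The conclusion rests on inferring staff knowledge from participant-only blinding and the fixed order, and on the timetable for the placement of the windows. The point merits a change because the remedy is cheap.

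**What to change.** At every visit before Visit 6:
- Staff check diary completeness only. They do not show or discuss pain, activity, fatigue or mood ratings with the participant.
- The adverse-event and general-health interview in Minimization of Risks is kept, with the same neutral wording at every visit. The participant remains free to report any symptom.

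Separately, reconcile the Visit 5 text with the timetable on whether DXM continues after week 18, so that the DXM window is defined.

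The cost is about a page of visit script and a sentence under each visit. The small downside is less informal discussion of symptoms. Staff would still know the treatment and the order would still be fixed, so this narrows the route rather than closing it.

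The SAP is dated 6/28/2022 and partly in the past tense. If data collection is complete, report the unblinded symptom review as a limitation of the primary result.

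### Visit 5 dispenses 30 more days of DXM although the timeline makes the next two weeks drug-free, so neither DXM exposure nor the SAP's final four-week DXM window is settled

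*Protocol*

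**What the plan says.** **Dispensing (Protocol, Study Visits).** At Visit 3 participants "receive DXM for approximately the next 5 weeks". At Visit 4, if there have been no adverse events, "the participant will receive the next dose of DXM to take for 5 weeks". At Visit 5, on the same condition, "the participant will receive the normal dose of DXM to take for 30 days", and the diary continues.

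**End of study (Protocol, Visit 6).** "Approximately Two weeks after visit 5 the participant will return to the CRU or Campbell Hall to turn in their handheld device". At that visit staff also "un-blind the participant to which medications were received during the study". The section adds: "A +/- 3 day study visit window will be implemented for all study visits".

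**Schedule (Protocol, Study Timeline).** DXM occupies weeks 9 to 18, with Visit 5 in week 18. Weeks 19 and 20 are labelled as a no-drug baseline. Hepatic and renal draws are listed at Visits 4 and 5. The Visit 6 row reads "Blood for assays". Participation lasts about 20 weeks in total.

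**Risk text (Protocol, Minimization of Risks).** A treatment duration of 10 weeks is listed among the measures that limit risk. The rule on returning unused medicine, just before the Study Timeline, covers only participants who are terminated.

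**Primary outcome (SAP).** Daily general pain is compared between the final four weeks on placebo and the final four weeks on DXM. No week numbers or study days are given.

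**The concern.** The Visit 5 text and the timeline cannot both be followed. One hands out DXM; the other makes the same period drug-free. The sentence is complete and the table rows are legible, so this is not damage from the PDF.

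It is also a dosing instruction. Staff working from the visit descriptions would dispense drug in a period meant to be off drug, and would exceed the duration that the protocol offers as a safeguard. The timeline shows no hepatic or renal draw after Visit 5.

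The conflict also reaches the primary outcome. The SAP's DXM window is counted back from the end of DXM treatment, so moving that end moves the window. From the documents alone, a reader cannot tell which diary days were compared.

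**Working it through.** **Inputs.** Visit 3 supply 35 days; Visit 4 supply 35 days; Visit 5 supply 30 days; Visit 5 to Visit 6, 14 days; visit window 3 days either way. DXM day 1 is the first day of week 9.

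**The plan's own figure.** Weeks 9 to 18 are 10 weeks, or 70 days. The Visit 3 and Visit 4 supplies give 35 + 35 = 70 days. The phases add up: 1 screening + 2 baseline + 5 placebo + 10 DXM + 2 off drug = 20 weeks. The 10-week duration and the 20-week total therefore reproduce without any Visit 5 supply.

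**Exposure and final 28-day window.** The window is counted back from the last DXM day. Diary days are those up to device return, at about DXM day 70 + 14 = 84.

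| Schedule | DXM days | Change from 70 | Final 28 DXM days | Diary days | Shared with days 43-70 |
|---|---|---|---|---|---|
| Timeline | 70 | none | 43-70 (weeks 15-18) | 28 | 28 |
| Visit 5 supply, stop at Visit 6 | 70 + 14 = 84 | 84/70 = +20% | 57-84 (weeks 17-20) | 28 | 14 (days 57-70) |
| Visit 5 supply, finished | 70 + 30 = 100 | 100/70 = +43% | 73-100 | 12 (days 73-84) | 0 |

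**Supply left at Visit 6.** 30 - 14 = 16 days.

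**Effect of the visit window.** Visit 6 is timed from Visit 5. If that gap g runs from 11 to 17 days:
- exposure at Visit 6 is 70 + g = 81 to 87 days;
- supply left is 30 - g = 13 to 19 days;
- the first two windows share 28 - g = 11 to 17 days;
- diary days in the third window are g - 2 = 9 to 15.

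If both visits instead move from their nominal dates, g is 8 to 20 and supply left is 10 to 22 days.

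**Which windows can be analysed.** The outcome is a daily self-report. The third window has 28 - 12 = 16 days after the device is returned and the participant is un-blinded, so it cannot be analysed as written. Two readings remain, weeks 15-18 and weeks 17-20. Weeks 15-18 are on drug, blinded and covered by the diary whichever schedule was used.

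**The case against.** The strongest reply is that the sentence is leftover text. Visits 3 and 4 supply exactly the 10 weeks in the timeline, and the 20-week total leaves no room for 30 more days. Other stray references point the same way: Visit 6 mentions a visit 10, and the risk sections list draws at visits 1, 3, 6 and 9 in a six-visit study. This is the likeliest explanation, and it stands as such. But no passage says so. The Biospecimens section counts three draws in the drug monitoring phase, which by the timeline would be Visits 4, 5 and 6. That is a loose label, not a dosing instruction, so it is only slight evidence the other way.

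The safety argument has limits, and these stand too. The third supply is conditional on no adverse events, and the Background caps the daily dose at 20 mg. The 10-week statement is loose: it speaks of each treatment, although placebo lasts 5 weeks. The draw list in Minimization of Risks does include a visit 6, though the list does not fit this schedule. The documents give no duration at which harm is expected.

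A reader might infer three stronger things that the documents do not support:
- *That participants took 100 days of DXM.* This would require 16 days of dosing after the final interview and un-blinding. Nothing shows that even the extra supply was given.
- *That the primary window has three usable readings.* The third lacks diary data for 16 of its 28 days.
- *That the primary comparison is contaminated.* Off-drug days enter only if weeks 17-20 were analysed although the timeline was followed. Using weeks 15-18 is sound under either schedule, and no SAP analysis is defined on weeks 19-20 or on the Visit 6 assays.

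**Conclusion.** The contradiction is real and unresolved, and it must be corrected because it is an operative dosing instruction. If the Visit 5 text is followed, DXM exposure by Visit 6 is about 84 days instead of 70 (+20%; 81 to 87 with Visit 6 timed within 3 days of its target after the actual Visit 5). The outer bound is 100 days. The two off-drug weeks are lost, and about 16 days of supply are left without a return rule for completers.

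For the primary outcome, the damage is ambiguity, not demonstrated bias. Two analysable windows exist, and they differ in 14 of 28 days.

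These figures assume uninterrupted dosing from the start of week 9 and exactly 70 DXM days by Visit 5.

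**What to change.** First, state which schedule was followed after Visit 5 and which days entered the primary comparison. The SAP describes the analyses in the past tense, so this is a statement of fact, not a new design choice.

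**If the timeline was followed:**
- Replace the Visit 5 sentence with: *no study drug is dispensed; unused DXM is returned; diary reporting continues off drug to Visit 6.*
- In the SAP, define each primary window as the 28 days ending on the participant's last scheduled dose of that treatment, nominally weeks 15-18 for DXM and weeks 5-8 for placebo. Exclude days after the supply ended.
- Do not anchor the window to the visit date. If Visit 5 falls 3 days late on a 35-day supply with no spare doses, the last 3 of the 28 days before it are off drug.

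**If DXM was given after Visit 5:** correct the timeline rows for weeks 19-20 and the 10-week statement. Keep weeks 15-18, or state another window that ends before un-blinding at Visit 6.

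**Cost.** One statement of the schedule used, one protocol sentence replaced and one SAP definition added. In the second case, two timeline rows and the 10-week statement also change. No new visits or data are needed.
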